Protocol Title: Acceptability of HPV self-sampling tools for cervical cancer prevention in Jamaican women: A theory-based approach to culturally-tailored message design.

Version: 1A

Version Date: April 27, 2018

NCT Number: NCT03613493

1) Protocol Title

Acceptability of HPV self-sampling tools for cervical cancer prevention in Jamaican women: A theory-based approach to culturally-tailored message design.

2) IRB Review History*

N/A

3) Objectives*

The purpose of the proposed study is to increase HPV screening behaviors in Jamaican women by examining the acceptability of HPV DNA self-sampling tools, and determine the most culturally appropriate and effective message design for promoting such a tool in this context.

Specific Aim: Evaluate culturally-tailored HPV DNA self-sampling toolkit.

H1: Women who receive culturally tailored messaging will exhibit improved screening, screening-relevant knowledge, attitudes, and perceived-efficacy.

4) Background*

Low screening coverage is related to health system barriers, as well as women's attitudes and knowledge about cervical cancer screening. In a study conducted by the Ministry of Health and Environment of Jamaica in 2008, lack of uptake was found to be influenced to a significant degree by fears and misconceptions on the part of Jamaican women, including ideas that the human papillomavirus (HPV) test causes damage to the cervix. In addition, other factors impeding women in Jamaica include concerns about privacy, belief that the procedure was embarrassing, ignorance about where to get a pap test, and lack of sufficient information, fear of pain, fear of cervical cancer diagnosis, and lack of sufficient time with their doctors.

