The US Food and Drug Administration has designated HPV screening as a best practice in identifying risk of cervical cancer, over and above pap test screening, because of its high efficacy, affordability, and convenience, since it can be adapted for various settings. The HPV self-sampling tool has been shown to address issues such as privacy, and studies have shown that women feel more comfortable with this option and expressed willingness to recommend the tool to others. This adaptability has become a driving force in advocates support for the tool in hard-to-reach and poor areas. HPV self-sampling has been tested in many contexts, including resource-limited countries, and has been found to be efficacious and cost-effective. With this now fairly well-established in the literature, research questions have now focused on the best strategies for diffusion of the tools. It has been suggested that Community Health Workers (CHWs), coupled with Community-based Participatory Research (CBPR) methods are the ideal vehicle to ensure optimal uptake in community-settings. On the other hand, other studies have proposed that a mailed approach is preferred.

This current proposal aims to determine how culturally appropriate messaging within one context (Jamaica), alongside an innovation (self-sampling HPV test), might increase uptake of screening behaviors.

5) Inclusion and Exclusion Criteria*

Rationale for inclusion/exclusion criteria: This study will involve the collection of data from Jamaican women. Eligible participants will be accepted to the study on a first-come- first-serve basis. A prescreening survey in person or over the phone (see Appendix A), as well as the data from the baseline survey (see Appendix B), which will include a demographic section which will include self-reporting of age etc. (listed below) which will be an additional check for confirming eligibility for the study.

Inclusion criteria: Jamaican women, aged 30 to 65.

Exclusion criteria: women who report having had a hysterectomy, have had a history of cervical cancer, Women who are currently up-to-date on cervical cancer screening (have had a Pap in the last 3 years or have had a Pap smear/HPV co-test within the past 5 years), adults unable to consent, children, pregnant women and prisoners.

6) Number of Subjects*

Total expected: approximately 360 participants, (350 for the intervention; 10 interviews)

7) Study-Wide Recruitment Methods*

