Jamaican women will be recruited for participation in two different phases of this research project. Efforts will be made to include women from rural areas, urban areas, and varying socio economic and cultural backgrounds. Recruitment will occur in three identified low-screening regions in Jamaica (using national statistical data on screening rates per parish in Jamaica), and enrolment will take place through local community organizations as well as at community events such as health fairs.

8) Study Timelines*

An individual subject in the research is expected to participate up to maximum of 4 months. Enrolling study subjects is expected to not exceed one month prior to the actual study date. The estimated date for the investigators to complete this study is September 30, 2018. The primary data analysis will be completed by October 31, 2018. Other studies that have utilized community and government partners have been successful at recruiting a similar number of participants over a short time. For example (Barrett & Huffman, 2011) collected their entire dataset in 3 weeks in October 2007 (276 Jamaican adolescents). Another example is (Lewis-Bell et al., 2013), a cross-sectional study that

took place in April–July 2010 with 852 sexually-active Jamaican women, 16–49 years of age.

9) Study Endpoints*

The primary study endpoints are:

- Development of messages and design of HPV self-sampling tool kit.

Based on formative results from interviews (see Appendix C for interview script), messages will be designed that are culturally appropriate and tailored for any audience segments which emerge from the data. Feedback will be used to design a culturally adapted HPV DNA self- sampling toolkit for this context.

- Evaluation of culturally-tailored HPV DNA self-sampling toolkit.

Enrolled participants will complete a pre-test/baseline questionnaire which will be based on the theoretical constructs identified, and which will also be assessed in the posttest. The intervention will be considered a success when: 1) the majority of women targeted opt to return their sample, as instructed on the toolkit, for testing and, 2) upon evaluation (posttest - See Appendix C), women report higher levels of, knowledge, self-efficacy and response efficacy or positive changes in attitudes toward screening than at baseline.

10) Procedures Involved*

Interviews

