Participants will receive the HPV self-sampler at the time they complete the baseline survey with the Co-I/local study coordinator. The HPV self-sampler kit will include the collection swab and the vial for collecting and storing the specimen, and an instructional sheet that visually depicts the steps for self-sampling. 115 women will receive a culturally-targeted, fear appeal message for the HPV self-sampler kit; 115 women will receive only a fear appeal message, not targeted for the Jamaican populace; and 115 women will receive only the self-sampler tool with no message appeal (plain packaging). (Appendix G & J). The Co-I/local study coordinator will offer the HPV self-sampler accompanied by an instruction sheet on how to use the self-sampler. At this point participants will receive some sensitization on the topic, which will include: 1) health education on the importance of cervical cancer screening using a short intervention/educational script (Appendix H) and 2) motivation to encourage women to have screening using the HPV self-sampler. Women will also be informed of the following: 1) HPV infection usually is not detectable or harmful; 2) nearly everyone who has had sexual intercourse has been exposed to HPV and infection is very common; 3) a positive HPV test result does not indicate the presence of cancer and that not all women who test positive for an HPV infection will not develop advanced cancer. It will also be stressed to women that if they have not seen a doctor recently they will still need to see a provider to address other health issues, which may include a gynecologic exam. They will also be advised that if HPV obtained through self-sampling is positive, they will need follow-up medical care at clinical sites (a list of possible sites will be provided). and to package and return it by mail or to the address provided. A brief survey on intentions will then be administered (Appendix K). Participants will be asked to use the tool at home by following the instructions, The local study coordinator will follow up with participants who do not return the kit within 1 week via SMS messaging. All participants will receive the following message: "Please remember to return your HPV self-sampler kit to X location during the following times: X Y, and Z. Please ignore this message if you have already returned the kit. Thank you."

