All data will be inspected for quality assurance prior to analysis. Prior to performing statistical analysis on quantitative data, the data will be checked, screened and verified. Data checking is critical to ensure the integrity of the database. Range checks will be routinely performed, and random items from the raw data will be checked against the entered data so that mistakes can be identified. the sampling strategy for our study may be described as purposive and snowball sampling. Women will not be not randomly selected as the study was intended to capture a community-based population that meets specific selection criteria. Data will be analyzed from interviews using the constant comparison method (Corbin & Strauss, 2008). For the message design experiment, a paired t-test will be conducted to determine the difference between pre and posttests in screening behavior after exposure to the self-sampling tool; mediation analyses will be conducted to determine if change in screening knowledge, attitudes and perceived-efficacy mediated changes in screening outcomes. Mediation analyses

will be performed using ordinary least squares regression, using techniques recommended for within-subject designs (Judd, Kenny, & McClelland, 2001).

To maintain participant confidentiality, study specific ID codes are used in all study tracking and analyses. Only the Co-I/local study coordinator will have access to the files linking participants with study ID numbers.

13) Provisions to Monitor the Data to Ensure the Safety of Subjects*

All study data collected will be uploaded into the REDCap system. As previously stated, the Co-I and local coordinator have access to this system to enter participant data using an iPad or paper-based methods during interviews and site visits, and in real time during the evaluation phone call.

Furthermore, quality and completeness of data entry will be systematically checked by a data manager at regular intervals for the duration of the study. Only the Co-I has access to the raw data files entered by the Co-I/local study coordinator. De-identified data files that have been cleaned and appropriately grouped and categorized will be made available to study personnel requesting such data.

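### Success criterion 2 is a pre-post rule with no comparator arm, no test level and an ambiguous and/or, so meeting it would not show that the tailored message worked.

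*Combined protocol and SAP*

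**What the plan says.** Section 9 (Study Endpoints) sets two conditions for calling the intervention a success. The first is that "the majority of women targeted opt to return their sample, as instructed on the toolkit, for testing and", with the closing *and* joining it to the second. The second, criterion 2, is that at posttest "women report higher levels of, knowledge, self-efficacy and response efficacy or positive changes in attitudes toward screening than at baseline".

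H1 in Section 3 (Objectives) concerns women who receive culturally tailored messaging and predicts "improved screening, screening-relevant knowledge, attitudes, and perceived-efficacy".

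Section 10 (Procedures Involved) describes three groups of 115: a culturally targeted fear appeal, an untargeted fear appeal, and plain packaging. It then describes what participants receive with the kit, including "health education on the importance of cervical cancer screening using a short intervention/educational script", and does not restrict this to any group. The posttest is given when the kit is returned.

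The analysis text is in Section 12 (Data Management). It says that "a paired t-test will be conducted to determine the difference between pre and posttests in screening behavior after exposure to the self-sampling tool", and that mediation analyses will examine "if change in screening knowledge, attitudes and perceived-efficacy mediated changes in screening outcomes". It gives no significance level and no comparison between the three groups.

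**The concern.** The Specific Aim is to evaluate the tailored toolkit, and H1 is about women who receive tailored messaging. Criterion 2 compares women only with their own baseline. If the education script, or simply using the kit, raises scores in every group, the criterion can be met when tailoring adds nothing.

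Two further weaknesses lie in the wording. The *or* lets a change in attitudes stand in for the other constructs, which H1 does not allow. The order of *and* and *or* is not fixed and no threshold is given, so the reading could be chosen after the data are seen. At stake is whether a declared success says anything about the tailored message.

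**Working it through.** The documents give no alpha, power or sample-size calculation, so there is no stated figure to reproduce.

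**Step 1. What a pre-post rule can show.** For one construct, let *d* be the mean rise that every group shares (script, kit use, repeated questionnaire) and *t* the extra rise due to the tailored message.
- Change from baseline in the tailored group: *d* + *t*. This is positive whenever *d* > 0 and *t* = 0.
- Tailored minus comparator: (*d* + *t*) − *d* = *t*.

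Only the second quantity bears on H1. This step assumes that the script follows the baseline survey. Section 10 places it at kit handover, which coincides with completing that survey.

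**Step 2. Whether Section 12 supplies the missing test.** It does not. The paired t-test concerns screening behavior and has no level. Knowledge, attitudes and efficacy appear only as mediators.

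**Step 3. How far the reading matters (illustration only).** Inputs not in the documents: a positive group-mean change is enough; there is no true change, so each construct has probability 0.5 of a positive mean change; the common correlation is 0 or 0.5. Sample size does not matter, because a sign rule has null probability of about 0.5 at any n. Write K, S, R and A for knowledge, self-efficacy, response efficacy and attitudes. At correlation 0.5, the chance that *k* constructs are all positive is 1/(*k* + 1): 1/4 for three and 1/5 for four.

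| Reading | Independent | Correlation 0.5 |
|---|---|---|
| (K and S and R) or A | 1 − (1 − 1/8)(1 − 1/2) = 56.25% | 1/4 + 1/2 − 1/5 = 55% |
| Any of the four | 1 − (1/2)^4 = 93.75% | 1 − 1/5 = 80% |
| K and S and (R or A) | 1/4 × 3/4 = 18.75% | 1/4 + 1/4 − 1/5 = 30% |
| All four | (1/2)^4 = 6.25% | 1/5 = 20% |

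A simulation of 2,000,000 draws agrees: at correlation 0.5 it gives 54.9%, 80.0%, 29.9% and 19.9%. The first reading falls slowly as the common correlation rises, to 54.0% at 0.7 and 52.3% at 0.9. If attitudes were independent of three constructs correlated at 0.5, it would be 1 − (1 − 1/4)(1 − 1/2) = 62.5%.

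**Step 4. The same rule with a test.** Test each construct at two-sided 5% and count only favourable results, so 2.5% each.
- Any of the four: 1 − 0.975^4 = 9.6% if independent; 7.8% at correlation 0.5 (simulated).
- (K and S and R) or A: 1 − (1 − 0.025^3)(1 − 0.025) = 2.5% if independent; 2.6% at correlation 0.5 (simulated).

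Multiplicity over constructs therefore matters on the any-of-four reading and hardly at all on the first.

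**The case against.** The strongest reply is that this is missing detail. Section 9 never says that the sign of a group mean is enough, so the percentages belong to a rule the reviewer supplied. They also assume no change, although a shared rise is what one would expect here. Both points stand against the percentages: they illustrate the ambiguity and do not measure the main problem. They do not answer Step 1. The rule as stated is a comparison with baseline, and adding a significance level would leave it unable to separate tailoring from the script.

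A reader might infer three stronger things that the documents do not support.
- *That about 55% is the chance of wrongly declaring success.* Success also requires majority kit return, and the documents give no basis for the probability of that.
- *That the criterion can hardly fail.* With no true change it fails 44% to 45% of the time on the first reading, and 81% or 70% on the third.
- *That four unadjusted tests give an error of 1 − 0.95^4 = 18.5%.* That figure counts significant worsening, whereas criterion 2 asks for improvement. Counting favourable results only, it is 9.6%, and only on the any-of-four reading.

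It is also fair to object that a between-arm comparison has limits here. The documents do not describe how women are allocated to the three groups, and posttest scores may exist only for women who returned the kit. This limits what the remedy can deliver but does not defend the present rule.

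**Conclusion.** The concern holds as a mismatch between the success rule and the hypothesis. Criterion 2 has no comparator arm, so it can credit the tailored kit with a rise that plain packaging would also show. It accepts attitudes alone where H1 lists the constructs together (taking H1's perceived efficacy to cover self-efficacy and response efficacy). Section 12 does not repair either fault.

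The central point needs only that the script reaches all groups after baseline, which is the natural reading of Section 10. The documents give no figure for the size of the shared rise, so the resulting error cannot be quantified. The ambiguity can be illustrated: 6% to 94% across readings with independent constructs, or 20% to 80% at correlation 0.5, for criterion 2 alone under a sign rule with no true change. The sponsor should correct this before analysis.

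**What to change.** In Sections 9 and 12:
- State one Boolean rule for criterion 2 that agrees with H1.
- Judge it on between-arm differences in posttest score adjusted for baseline (ANCOVA) for knowledge, self-efficacy, response efficacy and attitudes, each at two-sided 5%.
- Compare the tailored group with the untargeted fear-appeal group, which isolates tailoring, and with plain packaging, which captures the whole message. Name in advance which contrast decides success.
- If all four constructs must improve, no multiplicity adjustment over constructs is needed. If any one can suffice, use Holm over the four and amend H1 to match.
- Report all four with confidence intervals and keep the pre-post changes as descriptive.
- State how women are allocated to groups and that posttest scores may exist only for women who returned the kit. Report kit return and posttest completion by group.

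This costs a few sentences and uses data already planned. It does replace a within-woman criterion with a between-arm one, which is more than a change of wording. Success becomes harder to declare, and the contrast is only as unbiased as allocation and posttest completion allow.

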Narrative interviews: For the purpose of social science research, narrative interviews are unstructured and in-depth and ask participants to reconstruct a particular event that is important to them and their social context, in the format of a story, for an interviewer (Rohleder & Gibson, 2005). The method seeks to understand how people's narration of stories also demonstrates people's ways of thinking or their "unconscious logic" (Hollway, 2001, p. 15). Moving beyond the traditional question-response format, narrative interviewers have a diminished role. Instead the interview relies on certain expected schema in storytelling to elicit the sought-after rich data. This schema dictates that the respondent will naturally share the most pertinent information, provide sufficient detail, and include a structure that includes a beginning, middle and end of the main situation or occurrence being described. After the participants are asked to tell their story, the interview may not interrupt at any point to ask for further explanations or to express any opinions; the interviewee may only ask what happened next (Rohleder & Gibson, 2005). See Appendix C for interview script.

Tailoring the self-sampler messages (package and instructions): The participant responses will provide insight into local women's' perceptions, language, experience using the tool, which will further aid message design. The interviews will provide insight on the participants experience using the toolkit and how this is expressed linguistically. For example, in their own words how did they use the self-sampler tool. This will inform further the language and wording choices for the culturally-tailored condition.

Collection of Self-Samples:

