Determination of eligibility: Participants in the full intervention (350 women) will be screened for eligibility by the CO-I or a local study coordinator. The Co-I/local study coordinator will administer a brief screening questionnaire prior to obtaining informed consent (Appendix A). The screening questionnaire will cover the inclusion/exclusion criteria listed above. For women who screen potentially eligible, the CO-I/local study coordinator will further describe the study. Eligible potential participants will be told that we are conducting a research study to understand how new innovations like an at-home HPV self-sampling tool would be accepted by you and in your community. The study will involve completion of a baseline survey (Appendix B) about their sexual and reproductive practices and cervical self-sampling.

In our research, we plan to use a self-sampling device developed by Preventive Oncology International (POI) and the National Institutes of Health (NIH). The POI/NIH self-sampler is considered a non-significant risk device and has been approved for research conducted by NIH faculty throughout the United States and in various international settings. This device is manufactured by Puritan Medical Products, and is thought to reflect an improvement over other self-samplers, given a larger Collection Swab tip, which enables a woman to collect cells from more of

the cervix's total surface area with less effort. The POI/NIH self-sampler is a 20 cm in diameter, which is similar to a regular-sized tampon. This sampler is easy to use. A woman inserts the device into her vagina until she feels slight resistance. The participant then holds the paddle end of the Collection Swab and rotates it five times. She then withdraws the Collection Swab. Once the Collection Swab is fully removed from the vagina, the participant places the Collection Swab into liquid cell preservative and rotates it five times. The participant can then dispose of the swab in a household trash can and secure the vial lid. The participant should return the vial by mail (she will be provided a pre-addressed, stamped envelope) or in person to a specified return location. The CO-I/local study coordinator will be responsible for storing and shipment of the samples to the SCCC for testing.

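### The plan as supplied gives no method for assigning women to the three kit conditions and no between-arm analysis, so it cannot show which message design works best

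*Combined protocol and SAP*

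**What the plan says.** **Purpose.** Section 3 wants to "determine the most culturally appropriate and effective message design for promoting such a tool in this context". H1 reads: "Women who receive culturally tailored messaging will exhibit improved screening, screening-relevant knowledge, attitudes, and perceived-efficacy". It names no comparator.

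**Conditions.** Section 10 (Collection of Self-Samples) states that "115 women will receive a culturally-targeted, fear appeal message for the HPV self-sampler kit"; a further 115 get a fear appeal not targeted to Jamaica, and 115 get plain packaging. Earlier in section 10, on the interviews, the plan says "This will inform further the language and wording choices for the culturally-tailored condition". Sections 10 (Compensation) and 12 call this part a message design experiment.

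**Entry.** Section 5 says "Eligible participants will be accepted to the study on a first-come- first-serve basis". Sections 7, 21 and 24 describe recruitment in three regions through venues, recruiters' own networks and referrals of up to three women each. Section 12 says that women are not randomly selected.

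**Analysis.** Section 12 gives a paired t-test of pre against post, and mediation by least squares with within-subject techniques. Section 9 defines success as "the majority of women targeted opt to return their sample, as instructed on the toolkit, for testing", together with better knowledge, efficacy or attitudes than at baseline.

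**Numbers.** Section 6 gives "350 for the intervention; 10 interviews" and section 10 says "Participants in the full intervention (350 women) will be screened for eligibility".

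**The concern.** An objective about which message design is most effective calls for a comparison of the three kits. Two things are needed for that: a stated way of assigning women that makes the groups comparable, and an analysis that compares them. The supplied text has neither.

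The gap matters more here than in most studies. The same Co-I or coordinator finds the women, screens them and hands over visibly different kits. There are three regions and three conditions. If the stated analysis is followed, any improvement from baseline is likely to be read as a message effect, although it may come from what every woman receives. If someone later compares the arms, differences in who received which kit could produce or hide an effect, and adjustment after the fact cannot reliably repair that.

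**Working it through.** **1. Search for an assignment rule.** Section 10 fixes group sizes only. First-come, first-served (section 5) governs entry to the study, not to an arm. The mentions of randomness in section 12 concern the selection of women and the checking of data items. No unit, sequence, concealment or stratification is given. Arms filled by region, event, referral chain or recruiter choice would all comply with the text.

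**2. Search for an arm comparison.** The paired t-test contrasts each woman with herself. The mediation analysis is within-subject. The success rule in section 9 uses a majority and change from baseline. None has an arm term.

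**3. What a pre/post test can show.** Section 10 gives health education, motivation to screen and the SMS reminder to participants generally, with no exception for plain packaging. Suppose (assumption) that these shift scores by δ = 0.3 SD of the change score in every arm and that the messages do not differ. Power of the paired test is about Φ(δ√n − 1.96):
- n = 345: 0.3 × √345 − 1.96 = 3.61, power about 1.00.
- n = 115: 0.3 × √115 − 1.96 = 1.26, power about 0.90.

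A significant result is therefore expected with three equivalent messages, whether the test is run on all women or within one arm.

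**4. Size of possible confounding (illustration).** Assume 50% return, no message effect, 115 per arm, a two-sided 5% two-proportion z-test, and a 10-point difference in background return between two sources of women. If alignment of source with arm is partial, the spurious gap is 10 points × alignment:

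| Alignment | Spurious gap | False-positive rate |
|---|---|---|
| 25% | 2.5 points | 6.7% |
| 50% | 5 points | 11.8% |
| 100% | 10 points | 33.1% |

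No return rate, gap or alignment stands in the documents.

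**5. What an arm comparison could deliver.**
- 95% half-width for a difference near 50% return: 1.96 × √(2 × 0.25/115) = 0.129, about ±13 points.
- Power = Φ[(d − z·s0)/s1], where s0 = √(2p̄(1 − p̄)/n) and s1 = √((p1(1 − p1) + p2(1 − p2))/n). For 50% v 68.1%, d = 0.181, s0 = 0.0649, s1 = 0.0637. With z = 1.96 the power is 0.80. With z = 2.394 (5%/3, Bonferroni for three pairs) it is Φ(0.40), about 0.66.
- 50% v 60% has power 0.33, or 0.19 at 5%/3.

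**6. Counts.** The plan gives no power basis for 350, so it cannot be reproduced. 3 × 115 = 345, and 350 − 345 = 5 (1.4%).

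**The case against.** **The missing appendices.** Appendices G and J are cited beside the group sizes and were not supplied. An allocation procedure may stand there. This is fair, and it limits the first half of the point to the supplied text. It does not touch the analysis, which section 12 sets out.

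**H1 may be within-group.** H1 names no comparator, and section 9 measures success against baseline. A reader might infer that H1 cannot be tested without an arm contrast. The documents do not support that: H1 needs one only if read as comparative. The need rests on the objective in section 3 and the three-condition layout.

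**The analysis may be by arm.** A reader might infer that the t-test and the success rule pool all women. Neither section says so, and the women targeted in section 9 could mean the tailored group. The point survives, since separate pre/post tests by arm still do not compare arms (step 3).

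**Confounding is not shown.** A reader might infer that arms will be filled by region or chain. The text permits this but does not state it, and the words experiment and condition suggest deliberate assignment. Only the possibility stands.

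**Referral clustering.** A reader might infer large error inflation from long referral chains. The documents give a ceiling of three referrals per woman, no clear number of waves and no intraclass correlation, so no such figure is justified. For pre/post change, differencing may also remove stable chain effects.

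**Conclusion.** The point holds in this form: in the supplied text, assignment to the three conditions is unstated and no planned analysis compares them. The objective of finding the most effective message design is therefore not answered, and an arm comparison added later may be confounded. This should be settled before enrolment, because allocation cannot be repaired afterwards.

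The conclusion rests on the text, not on the illustrations. Under the stated assumptions, a shared 0.3 SD shift alone would make a significant pre/post result very likely, and partial alignment of a 10-point background gap with arm would raise a nominal 5% error to about 7% to 12%. The higher 33% needs full alignment, for which the documents give no evidence. The mismatch of 345 and 350 is minor. Confidence is medium, because of the appendices.

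**What to change.** 1. **Allocation.** At kit handover, after consent and the baseline survey, allocate each woman individually 1:1:1 from a concealed permuted-block list stratified by region. An existing team member who does not recruit should hold it; the data manager in section 13 may serve. Block the Co-I's REDCap rights to the list, since section 22 gives the Co-I recruitment, data management and analysis.
2. **Main analysis.** Replace the paired t-test with a between-arm comparison of kit return, adjusted for region, with all randomised women in the denominator. Define return as a vial received by a set date, because kits may be mailed. Section 14 destroys the data of women who withdraw, so return is not automatically known for everyone. Keep their arm and return status if consent allows; otherwise report withdrawals by arm.
3. **Contrasts.** Include all three pairs under a stated multiplicity procedure, for example an overall three-arm test followed by pairwise tests. Avoid a fixed order that makes tailored v plain depend on tailored v untargeted. At assumed returns of 68%, 59% and 50%, the first test has about 29% power, and the chance of claiming tailored v plain falls from about 80% to about 28%.
4. **Secondary.** Compare posttest scores between arms, adjusted for baseline and region. State that section 10 ties the posttest to kit return, so women who do not return a kit may have none.
5. **Referrals.** Record each woman's referrer and report chain-clustered standard errors as a sensitivity analysis.
6. **Counts.** Reconcile 345 with 350, for example as 117/117/116.

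**Cost.** All three kits must be carried to every venue, a list prepared and one field added. Precision is coarse, as step 5 of the working shows. Women in one chain may see each other's kits: losing 10% to 20% of an 18.1-point contrast would cut the unadjusted 80% power to about 71% to 60%.
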